#### *One week Run-In Period Risk*

Trial designs with a one-week placebo Run-In Period are well-established for T2DM trials. The patients will be maintained on stable antidiabetic therapy during the one-week Run-In

**Proprietary confidential information.**

© 2015 Boehringer Ingelheim International GmbH or one or more of its affiliated companies. All rights reserved.

This document may not - in full or in part - be passed on, reproduced, published or otherwise used without prior written permission.

Period and continue regular monitoring of blood glucose with a HBGM device. Thus, the risk of the one-week placebo treatment in this trial is considered to be minimal.

#### *Background Therapy and Study Medication Specific Risk*

Basal insulin is the stable background therapy in this trial. Patients are administered basal insulin and not short-acting insulin because there are fewer injections, lower risk of hypoglycaemia, and basal insulin covers postprandial peaks. Weight gain, hypoglycaemia, allergic reactions, injection site reaction, lipodystrophy, pruritus, and rash are the most common side effects noted with basal insulin. All patients will have received basal insulin and these events mainly occur shortly after insulin initiation (at least allergic reactions). For safety reasons, the basal insulin dose can always be modified by investigators.

Metformin, a typical background medication, is a drug that has been on the market for a long time, is widely used as a first line therapy, and therefore believed to be well characterized in terms of risk profile. Metformin can however cause lactic acidosis to develop, which is relatively infrequent and more likely to occur in patients who have kidney or liver disease, excessive alcohol use, X-ray or scanning procedures that require an injectable iodinated contrast drug, surgery, or a serious infection ([R10-5341](#), [R10-5537](#)). Patients may be taking metformin as part of their stable background therapy. With all these conditions being excluded and the monitoring throughout the trial, this risk will be minimal for patients taking linagliptin and metformin.

Alpha-glucosidase inhibitors (such as acarbose) may be used as background medication and decrease the absorption of carbohydrates from the digestive tract, thereby lowering the post-meal glucose levels. Alpha-glucosidase inhibitors are used to establish greater glycaemic control over hyperglycaemia in T2DM, particularly with regard to postprandial hyperglycaemia. Alpha-glucosidase inhibitors may be used as monotherapy in conjunction with an appropriate diabetic diet and exercise, or they may be used in conjunction with other anti-diabetic drugs. Alpha-glucosidase inhibitors commonly are associated with gastrointestinal side effects such as flatulence, bloating, nausea, vomiting, and diarrhoea.

Angioedema, urticaria and rash are listed as side effects for linagliptin (with any background, [R11-2588](#)). For the fixed dose combination of linagliptin plus metformin, the identified side effects correspond to the observed side effects of metformin (i.e., decreased appetite, diarrhoea, nausea, vomiting, and pruritus) plus the events for linagliptin on all backgrounds (nasopharyngitis, cough, hypersensitivity and pancreatitis as well as angioedema, urticaria, and rash). Furthermore, longer term safety data have not shown any further safety trends to date.

As with all drugs, the potential for hypersensitivity and allergic reactions has to be taken into consideration when linagliptin is administered. Other risks to the patients are the risks inherent to any clinical trial such as unexpected adverse clinical or laboratory events. Safety will be ensured by monitoring the patients for adverse events (AEs) both clinically and by laboratory testing. If any investigator should have a clinical concern, the safety of the patients will be of paramount importance.

**Proprietary confidential information.**

© 2015 Boehringer Ingelheim International GmbH or one or more of its affiliated companies. All rights reserved.

This document may not - in full or in part - be passed on, reproduced, published or otherwise used without prior written permission.

Approximately half of the patients participating in this trial may derive a direct benefit from being treated with an active compound and not a placebo. Patients who are not adequately controlled (whether in the blinded placebo or active compound group), as evidenced by FPG or blood glucose values (by HBGM device), will have adjustments to their background therapy or receive rescue therapy (according to [Section 4.2.1](#)) to ensure their safety.

Rescue therapy will be permitted in case of hyperglycaemia during the randomised treatment period if the defined criteria are met (refer to Section 4.2.1). The choice of rescue medication and its dosage according to Section 4.2.1 will be left to the discretion of the investigator and rescue medication will be taken in accordance with the local prescribing information of that respective medication. The use of rescue medication may be associated with relevant side effects, such as increase of hypoglycaemia risk, weight gain, etc.

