#### Criteria for Increasing, Adjusting, or Decreasing Permitted Antidiabetic Therapy

If the following FPG criteria are met and if further supported by HBGM results during the same time period, investigators may increase or adjust the patient's permitted antidiabetic therapy (i.e., the patient's background therapy of stable basal insulin prior to or after informed consent, and if applicable metformin and/or alpha-glucosidase inhibitor) for the treatment of hyperglycaemia ([R08-2669](#)):

#### Visit 3 to Visit 5

- The patient has a FPG level > 270 mg/dL [ $>15.0$  millimoles per Liter (mmol/L)] drawn by the study staff for the central lab after an overnight fast

#### Visit 5 to Visit 98

- The patient has a FPG level >240 mg/dL ( $>13.3$  mmol/L) drawn by the study staff for the central lab after an overnight fast

If the above criteria are met, the investigator should increase or adjust (e.g., by changing the timing of administration, etc.) the patient's permitted antidiabetic therapy to improve glycaemic control according to investigator's discretion and the changes should be documented in the eCRF.

If the patient is experiencing hypoglycaemia, the investigator should review the eDiary responses to diet and physical activity as well as the HBGM results to determine the

Proprietary confidential information.

© 2015 Boehringer Ingelheim International GmbH or one or more of its affiliated companies. All rights reserved.

This document may not - in full or in part - be passed on, reproduced, published or otherwise used without prior written permission.

appropriate approach to reduce occurrences of hypoglycaemia (e.g., encouraging the patient not to skip meals, increasing carbohydrate intake if increasing exercise, decreasing or adjusting the patient's permitted antidiabetic therapy).

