C3.1	Non-compliance with drug intake	Gross non-compliance issues only – based on compliance section of eCRF (at least two times on treatment compliance was outside 80-120% according to eCRF) Final decision at the DBL meeting (medical judgment).	PPS	E
C3	Non-compliance			
C3.2	Non-compliance with criteria for removal from trial	Criteria for removing a patient from the trial not adhered to. Final decision at the DBL meeting (medical judgment).	None	E
C3.3	Treatment interruption for more than 10 consecutive days	Documented treatment interruption for 11 consecutive days or more.	PPS	E
C3.4	Non-compliance with HBGM data collection	Compliance with completing HBGM < 50% and/or No tests performed for 5 consecutive days.	None	E
C4	Medication code broken			
C4.1	Medication code broken without just cause	Medication code broken for no valid reason. Final decision at the DBL meeting (medical judgment).	PPS	E
D	Concomitant medication			
D2	Prohibited medication use			
D2.1	Rescue medication taken without just cause	Use of rescue medication (as defined in Section 4.2.1 in CTP) with FPG prior to rescue therapy ≤240 mg/dL for Visit 3 to Visit 4 or ≤200 mg/dL for Visit 5 to Visit 98 and/or Review of eCRF for use of rescue medication without 6 week dose adjustment period (i.e. prior to Visit 4).	PPS	E
D2.2	Antidiabetic drug taken that is not a protocol defined rescue medication and criterion to administer rescue medication not fulfilled	Antidiabetic drug other than protocol defined rescue medication taken and criterion for rescue therapy as in D2.1 not fulfilled.	PPS	E

* IPVs will be checked programmatically, including double programming checks for inclusion/exclusion criteria, where possible. IPVs where inclusion/exclusion criteria possibly need to be confirmed manually with respect to time A3.1, A3.4, A3.5, A4.1, A4.4, A4.5, A5.1, A5.3 and D2.3. For A1.2 dose changes may need to be checked manually. IPVs which can only be identified manually are A4.2, A4.3, A4.7, A4.8 and C3.2.

[figure not shown]
+ IPV-type: 'E' refers to efficacy IPV, 'S' refers to safety IPV and 'R' refers to general (regulatory) IPV.

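### Protocol 4.2.1 puts the Visit 5 FPG sample in two intervals with different limits, and SAP item D2.1 judges rescue against limits that match neither 4.2.1 criterion

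*Protocol*

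**What the plan says.** Protocol 4.2.1 sets the condition for raising background therapy: "If the following FPG criteria are met and if further supported by HBGM results during the same time period, investigators may increase or adjust". It gives two limits. For "Visit 3 to Visit 5" the condition is "The patient has a FPG level > 270 mg/dL"; for "Visit 5 to Visit 98" it is "The patient has a FPG level >240 mg/dL". No sentence says to which interval the Visit 5 sample belongs. A later sentence on the same step reads "If the above criteria are met, the investigator should increase or adjust".

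The same section has a separate criterion for starting additional rescue medication: FPG not brought down to 270 mg/dL or lower after a 6-week dose-adjustment period, so no earlier than Visit 4. It also classes some background changes as rescue therapy: basal insulin increases above 50%, 30% or 20% (depending on the baseline dose) for more than 7 days, and any increase in metformin or alpha-glucosidase inhibitor.

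SAP Table 6.2: 1, item D2.1, lists as an important protocol violation "Use of rescue medication (as defined in Section 4.2.1 in CTP) with FPG prior to rescue therapy" at or below 240 mg/dL (Visit 3 to Visit 4) or at or below 200 mg/dL (Visit 5 to Visit 98). It adds use of rescue medication without the 6-week adjustment period. The consequence is exclusion from the per-protocol set.

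Protocol 2.3 summarises the safeguard, and points to section 4.2.1 for its terms: patients not adequately controlled, "as evidenced by FPG or blood glucose values (by HBGM device), will have adjustments to their background therapy or receive rescue therapy".

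**The concern.** The documents hold three sets of FPG limits for closely linked decisions, and one set overlaps itself. At Week 12 a site cannot tell from the protocol which limit governs the sample it has just drawn. Some of the resulting increases count as rescue. Protocol 7.4.1 and SAP 6.6 set HbA1c after rescue to missing in the primary analysis, so the reading that a site chooses can decide whether a Week 24 value is used.

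D2.1 is meant to catch rescue given outside the protocol's criteria. If its limits sit below those criteria, it misses some of that rescue, and the per-protocol set is then less strict than its name suggests.

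**Working it through.** **Inputs.** Limits and intervals: protocol 4.2.1. Violation limits: SAP Table 6.2: 1, D2.1. Visit 5 is Week 12, Day 85, with a scheduled FPG (Flow Chart). Sample size: protocol 7.6 (SD 1.2%, difference 0.77%, 150 per arm, two-sided 5%).

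**1. The plan's own figures.** Units: 270/18.016 = 15.0 and 240/18.016 = 13.3 mmol/L, as printed. Power: SE = 1.2 × √(2/150) = 0.1386; 0.77/0.1386 = 5.557; Φ(5.557 − 1.960) = 99.98%, which agrees with the stated value above 99%. The point does not depend on this figure; it is used in step 4.

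**2. Visit 5.** Read as the end of the first interval, the sample must exceed 270 mg/dL. Read as the start of the second, it must exceed 240 mg/dL. A value above 240 and up to 270 mg/dL fails the first reading and meets the second.

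**3. D2.1 beside the protocol criteria (mg/dL).**

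| FPG taken at | 4.2.1: increase background therapy | 4.2.1: start rescue medication | D2.1 flags | Fails a 4.2.1 limit, not flagged on FPG |
|---|---|---|---|---|
| Visit 3 | >270 | not before Visit 4 | ≤240 | >240 to 270 (rescue medication this early is flagged on timing) |
| Visit 4 | >270 | still >270 after 6 weeks | ≤240 | >240 to 270 |
| Between Visits 4 and 5 | >270 | still >270 | no limit, read literally | up to 270 |
| Visit 5 | >270 or >240 | still >270 | ≤200 | >200 to 240 on either reading; >240 to 270 on one reading, or against the rescue criterion |
| After Visit 5 | >240 | still >270 | ≤200 | >200 to 240 (increase); >200 to 270 (rescue medication) |

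The unflagged band is 270 − 240 = 30 mg/dL wide at Visits 3 to 4. From Visit 5 it is 240 − 200 = 40 mg/dL against the later adjustment limit and 270 − 200 = 70 mg/dL against the rescue-medication criterion. The mismatch runs one way: every FPG that D2.1 flags also fails the protocol limits, so the FPG limb flags too little, never too much. D2.2 refers back to the D2.1 criterion and inherits the mismatch.

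**4. Size of the Visit 5 band.** The documents give no FPG distribution. Assume a normal distribution with mean 140 to 180 and SD 40 to 55 mg/dL. The share in the band is Φ((270 − μ)/σ) − Φ((240 − μ)/σ).

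- μ = 140, σ = 40: 0.0062 − 0.0006 = 0.0056 (upper tails), or 1.7 of 300.
- μ = 180, σ = 55: 0.1377 − 0.0509 = 0.0868, or 26.0 of 300.

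This is a ceiling under those assumptions: the band matters only if home readings support an increase, and HbA1c is affected only if the increase counts as rescue. For 99% power the plan's inputs need 2 × (1.960 + 2.326)² × (1.2/0.77)² = 89.2, so 90 per arm. Even if all 26 lost their Week 24 value and all were in one arm, 150 − 26 = 124 would remain.

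**The case against.** Four objections have force.

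**Section 2.3 is only a summary.** A reader might infer that it promises a home-glucose-only safeguard that 4.2.1 withholds. The documents do not support that. The sentence defers to 4.2.1. Section 2.3 also says that investigators can always modify basal insulin for safety, 4.1.4 leaves background changes for hyperglycaemia to their discretion, and Flow Chart footnote D provides for a repeat FPG. Counting the 42 × 4 = 168 scheduled home readings between FPG visits measures readings, not disputed decisions. What stands is that the summary is looser than the rule. The shift from permissive to directive wording within 4.2.1 is drafting style, since the directive sentence still leaves the change to the investigator's discretion.

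**The overlap does not cost patients their place in the per-protocol set.** A reader might infer that it does. A value above 240 and up to 270 mg/dL exceeds both D2.1 limits, so the FPG limb removes nobody in that band. It is also unclear whether D2.1, which speaks of rescue medication, covers background increases that count as rescue therapy.

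**No bias between arms follows.** Sites are blinded, so a site's reading of Visit 5 applies to both arms. Rescue may well be more frequent on placebo, and SAP 6.6 concedes that the observed-cases approach can be non-conservative when data are missing for lack of efficacy. Both come from the rescue strategy and would remain with perfect wording.

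**The D2.1 limits may be a deliberate tolerance.** The SAP history table records that FPG limits in section 6.2 were adjusted, so they were considered. But the SAP gives no reason, and D2.1 itself points to protocol 4.2.1 for its definition. If a margin is intended, it should be stated.

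**Conclusion.** The contradiction is real and limited. The Visit 5 sample falls under two limits, and D2.1 uses limits and a visit split that match neither the adjustment rule nor the rescue-medication criterion. The first affects background adjustments around Visit 5, some of which count as rescue and set later HbA1c to missing. The second affects the per-protocol set, which SAP Table 6.3: 1 uses only for a sensitivity analysis of the primary endpoint. There the effect is under-flagging.

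The range of 2 to 26 of 300 patients rests wholly on assumed FPG distributions and on all 300 having a Visit 5 sample; the number whose management or data would actually change is smaller and unknown. The power conclusion rests on the plan's own difference and SD. The difference in wording between 2.3 and 4.2.1 is minor. The point is worth correcting because the text can be read two ways, not because the primary result is at risk.

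**What to change.** Reconcile the passages:

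- In protocol 4.2.1, assign the Visit 5 sample to one interval.
- In protocol 2.3, word the trigger as 4.2.1 does.
- In SAP Table 6.2: 1, make the D2.1 limits and visit split match the reconciled criteria, cover samples between Visits 4 and 5, and say whether background increases that count as rescue therapy fall under D2.1. If a tolerance is intended, state it with its reason. D2.2 then follows.

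Which limit applies is for the clinical team. The cost is a few words in the protocol, a memo to sites and one SAP table row, with no new data and no change to the sample size or the primary model. The SAP row should be settled before unblinding, because it decides who is excluded from the per-protocol set.

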#### *Alternative Therapies for T2DM*

There are several alternative therapies available for the treatment of T2DM (e.g., biguanides, sulphonylureas, thiazolidinediones, sodium glucose co-transporter 2 (SGLT2) inhibitors, metglitinides, alpha-glucosidase inhibitors, rapid acting or short acting insulin); however, these are not without side effects. Side effects in the elderly population with thiazolidinediones include fluid retention, fracture risk, and heart failure risk. Side effects in the elderly population with sulphonylureas and metglitinides include hypoglycaemia. In the context of advanced age and diminished renal functions, cases of prolonged and severe hypoglycaemia with sulphonylurea treatment have been reported. Side effects in the elderly population with alpha-glucosidase inhibitors include gastrointestinal side effects. Side effects in the elderly population with rapid acting or short acting insulin include several injections and hypoglycaemia.

Thus, given the above considerations, the benefit-risk assessment for the use of linagliptin for the treatment of T2DM in elderly patients to improve glycaemic control is considered favourable for the conduct of this trial.

### 3. DESCRIPTION OF DESIGN AND TRIAL POPULATION

#### 3.1 OVERALL TRIAL DESIGN AND PLAN

This randomised, double-blind, multi-national, placebo-controlled, parallel group trial will compare linagliptin 5 mg daily to placebo as add-on therapy to a stable background of basal insulin, metformin (optional), and/or alpha-glucosidase inhibitors (optional) over 24 weeks in elderly T2DM patients with insufficient glycaemic control.

In total, approximately **300 T2DM patients (100 from Japan)**, 60 years of age and older, with insufficient glycaemic control will enter (i.e., be randomised in) this trial. The randomised treatment will be provided in a double-blind design within the two treatment arms (each patient will receive either linagliptin as active treatment or placebo matching linagliptin).

Patients are enrolled into the trial once they have signed the informed consent. The Screen Period is one week in length. All patients meeting the inclusion and exclusion criteria will complete a one week placebo Run-In Period before randomisation.

Patients who successfully complete the Run-In Period and still meet the inclusion and exclusion criteria will be randomised into the 24 week treatment period of the trial in which they will receive either linagliptin 5 mg or placebo.

[figure not shown]

Figure 3.1: Trial Periods

All adverse events with an onset after the first dose of study medication up to a period of seven days after the last dose of study medication will be assigned to the treatment phase for

**Proprietary confidential information.**

© 2015 Boehringer Ingelheim International GmbH or one or more of its affiliated companies. All rights reserved.

This document may not - in full or in part - be passed on, reproduced, published or otherwise used without prior written permission.

evaluation. This includes adverse events that start before first study medication intake and deteriorate under treatment. Other adverse events will be assigned either to the screening, run-in, or follow-up phase as appropriate. All adverse events, including those persisting after trial completion at the Post-Treatment Visit (Visit 99), will be followed-up for up to 7 days. The investigative staff should confirm if continuing adverse events have resolved or have been sufficiently characterised.

The end of the trial is defined as “last patient out”, i.e., last visit completed by the last patient.

### 3.1.1 Administrative structure of the trial

The trial is sponsored by Boehringer Ingelheim Pharma GmbH & Co. KG.

BI will appoint a Trial Clinical Monitor (TCM), responsible for coordinating the activities required in order to manage the trial in accordance with applicable regulations and internal standard operating procedures (SOPs), directing the clinical trial team in the preparation, conduct, and reporting of the trial, order the materials as needed for the trial, ensures appropriate training and information of CML, Clinical Research Associates (CRAs), and investigators of participating countries.

Data Management and Statistical evaluation will be performed by BI according to BI SOPs. For these activities, a Trial Data Manager and a Trial Statistician will be appointed.

Tasks and functions assigned in order to organise, manage, and evaluate the trial will be defined according to BI SOPs. A list of responsible persons will be given in the Trial Master File (TMF) document.

The organisation of the trial in the participating countries will be done by the respective local BI organisation [Operating Unit (OPU)] or a by a Contract Research Organisation with which the responsibilities and tasks will have been agreed and a written contract filed before initiation of the clinical trial. In each OPU participating in this trial, a CML will be appointed responsible for coordinating the activities required in order to manage the trial in accordance with applicable regulations and internal SOPs in the countries covered by the respective BI OPU.

A Co-ordinating Investigator will be nominated to coordinate investigators at different trial sites participating in this multicentre trial. Tasks and responsibilities for the Co-ordinating Investigator will be defined in a contract filed before initiation of the trial.

Documents on participating (Principal) investigators and other important participants, especially their curricula vitae, will be filed in the TMF.

A BI preferred central laboratory, ECG, and IRT provider will be selected to provide services for laboratory sample handling and analyses, ECG interpretation, and for study medication logistics, respectively as required for this protocol.

The eDiary and HBGM device will be provided by a BI preferred provider.

**Proprietary confidential information.**

© 2015 Boehringer Ingelheim International GmbH or one or more of its affiliated companies. All rights reserved.

This document may not - in full or in part - be passed on, reproduced, published or otherwise used without prior written permission.

Details on handling of the trial supplies including responsible institutions are given in [Section 4](#) of this protocol.

The Investigator Site File (ISF) will be kept in printed version at the trial sites as far as required by local regulation and BI SOP. A copy of the ISF documents will be kept as an electronic TMF document according to BI SOPs.

Based on the known safety profile, therapeutic window, and tolerability of linagliptin, a Data Monitoring Committee is not required for this trial.

